10.4.2.3 PD-1 and PD-L1 expression

An association of clinical response with the expression of PD-L1 AML BM cells will be assessed by a Pearson Chi-square test on a 2×2 table of frequencies. The dependent variable will be defined as response (yes *vs.* no), and QIF categories (negative *vs.* positive) will be the independent variables. We will also monitor the dynamic change of PD-L1 expression over the course of treatment and its correlation with clinical response. Longitudinal measurements of PD-L1 will be examined using mixed-effects modeling.

We will assess immune cell markers at different time points of therapy: at baseline (prior to application of 7+3 chemotherapy), at the end of consolidation, after 6 months and 1 year of treatment, and at relapse. We also plan to measure CD47 levels on leukemic blasts prior to and after chemotherapy and Pembrolizumab (MK-3475) administration to see whether CD47 expression levels correlate with responders *vs.* non-responders and whether expression levels change at different times of therapy. Statistical analyses of the frequency of CD8⁺, CD4⁺, FoxP3 T_{regs}, CD8⁺/FoxP3⁺ T_{regs}, T_{CM}/T_{EMRA}, T_{EM}/T_{EMRA}, the percentage of Ki67 and GzmB in PD-1⁺, Eomes⁺ CD8 T-cells to compare changes over time from baseline to several time-points will be performed by using mixed effects modeling with a Benjamini-Hochberg correction to control for false discovery rates.

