The expression of immune checkpoint seems to be only modestly elevated on AML cells at baseline but increases significantly, once AML cells are exposed to IFN- γ or chemotherapy and epigenetic therapy, as well as at the time of relapse either after chemotherapy or after bone marrow transplant (Kronig *et al.*, 2014; Sehgal *et al.*, 2015). Kronig *et al* demonstrated, in a cohort of 154 patients with AML, no significant increase in surface PD-L1 expression on leukemia cells at initial diagnosis compared to healthy controls (Kronig *et al.*, 2014). However, stimulation with IFN- γ significantly increased PD-L1 expression on AML blasts but not in normal controls. Highest upregulation of PD-L1 upon IFN- γ as measured was observed in patients with CR and with relapse whereas only slight upregulation upon IFN- γ was found in newly diagnosed patients. Yang *et al* showed that immune checkpoint expression was only modestly elevated on AML CD34⁺ cells at the time of diagnosis, however, was comparably higher when peripheral blood mononuclear cells (PBMCs) increased significantly once patients were treated with hypomethylating agents (Yang *et al.*, 2014). Looking at the mRNA levels in CD34⁺ cells from 32 patients with AML, they found that 15% had aberrant up-regulation (≥ 2 - fold) in PD-L1, PD-1, and CTLA4, respectively. However, expression of PD-L1, PD-L2, PD-1, and CTLA4 in PBMCs from AML patients was significantly higher. Upregulation (≥ 2 -fold) of PD-L1, PD-L2, PD-1, and CTLA4 was observed in 32%, 12.9%, 39%, and 3% of AML samples, respectively. Furthermore, treatment of leukemia cells with decitabine resulted in a dose- dependent upregulation of the above genes and patients resistant to therapy had relatively higher increments in gene expression compared with patients who achieved response. Exposure to decitabine resulted in partial demethylation of PD-1 in leukemia cell lines and human samples.

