2.5.4 Multiplex Immunofluorescence (mIF)

Immunohistochemistry is one of the most acceptable tools to measure PD-1 and PD-L1 expression in tumor microenvironment (TME). Human BM core biopsy will be decalcified for immunohistochemistry (IHC). We will compare IHC/IF findings and its quantitative analyses by using Multiplex Immunofluorescence (mIF) (will be describe below) with flow cytometric data in BM aspirate and blood. All these procedures will be performed with a collaboration with [name] [name] at MDACC CIMAC. For multiplex IF image analysis platform, we will use the tyramide signal amplification (TSA) methodology through the Opal™ workflow and chemistry which allows simultaneous staining of multiple biomarkers within a single paraffin tissue section. The multispectral microscopy Vectra™ and Vectra-Polaris™ scanner systems

(Akoya Biosciences, Waltham, MA, USA) including the image analysis software (InForm, Akoya Biosciences) allows the analysis of the multispectral images generated by this staining methodology. Multiplex ImmunoFluorescence (IF) staining will be performed on FFPE tumor slides using the following panels and antibodies:

1. **Panel 1 (PD-L1/PD-1 and TIL Panel):** PD-L1, CD68, PD-1, CD8, CD3, PanCytokeratin, DAPI.
2. **Panel 2 (T cell Activation/ Regulatory Panel):** FOXP3, Granzyme B, CD45RO, CD8, CD3, PanCytokeratin, DAPI.

2.5.5 Dynamic change of immune cell subsets:

We will possibly have limited number of cells in the BM aspirate. Therefore, we will analyze the immune profile combining a high-throughput technique that will allow us to study more than 20 markers in a single cell analysis using CyTOF. These techniques will provide information about the architecture of TME (*i.e.* BM) and the distribution of markers of interest detected with CyTOF. CyTOF-based single cell analysis is a new technology that combines flow cytometry with metal-conjugated antibodies detected by mass spectrometry permitting higher order multiplexing (up to 100 molecules) on a single cell analysis (Bendall *et al.*, 2011). Additionally, after fixation and permeabilization, cells will be stained with anti-human Ki-67-151Eu (B56;BD Pharmingen Ab conjugated with lanthanide MaxPar Europium Chloride 151Eu using the MaxPar X8 Ab labeling kit) for 30 min at room temperature. Cells will be acquired on CyTOF 2 instrument (DVS; Fluidigm Sciences). All data will be analyzed, and graphs generated using the DVS Cytobank software (Cytobank).

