The primary outcome of interest is to longitudinally characterize microbial shifts in patients with AML receiving PD-1 inhibitors. For this analysis standard of care will be compared with the experimental arm which includes chemotherapy + Pembrolizumab (MK-3475) combination. Secondary outcomes of interest will be a measure of both efficacy and toxicity which will include variables like rates of CR/CRi, progression free survival (PFS), overall survival (OS), cumulative incidence of graft versus host disease (GVHD)/non-relapse mortality (NRM). Association between microbial diversity on the percentage of patients with minimal residual disease (MRD) negative complete remission (CR) (MRD-CR) as measured by flow cytometry at the end of first consolidation cycle will also be explored.

Exploratory outcomes:

Correlation between microbial/metabolome changes with immune-checkpoint expression and kinetics of immune cell subset recovery and programming in the standard of care and experimental arm will be evaluated. As a marker of mucosal immunity, changes in immune cell content within stool samples in patients that experience colitis or GI-GVHD will be compared to suitable controls.

Part 1: Assess whether baseline biomarkers or the serial measurements of biomarkers are associated with response outcomes.

A univariate logistic regression will be selected to assess baseline biomarkers associated with response outcomes. The dynamic changes of PD-L1/ PD-1 expressions, concentration of cytokine, RNA seq/TCRseq, gut microbiome, etc. will be monitored. The measurements of biomarkers in changes over time from baseline to several time-points will be performed by using generalized linear mixed effects modeling with a Benjamini-Hochberg correction (Benjamini *et al.*, 1995) to control for false discovery rate.

Part 2: Assess whether baseline biomarkers or the serial measurements of biomarkers are associated with survival outcomes.

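### The one PD-L1-specific response test cuts a quantitatively imaged marker to negative/positive at an unstated cut-off; a logistic regression on the continuous score should lead

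*Combined protocol and SAP*

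**What the plan says.** - **The test.** Section 10.4.2.3 states that the association between clinical response and PD-L1 on marrow AML cells "will be assessed by a Pearson Chi-square test on a 2×2 table of frequencies".
- **The coding.** In the same paragraph, "The dependent variable will be defined as response (yes *vs.* no"), and "QIF categories (negative *vs.* positive) will be the independent variables". QIF is not defined there, and no cut-off, significance level, effect size or power is given.
- **The assay.** Section 2.5.4 describes image-analysis software and "We will compare IHC/IF findings and its quantitative analyses by using Multiplex Immunofluorescence (mIF"). PD-L1 is in Panel 1.
- **Other PD-L1 analyses.** Section 10.4.2.3 adds: "Longitudinal measurements of PD-L1 will be examined using mixed-effects modeling". Part 1 of the exploratory outcomes (at the end of 10.4.2.8) says: "A univariate logistic regression will be selected to assess baseline biomarkers associated with response outcomes". It does not say whether the marker enters as a continuous score or as a category. Neither section refers to the other.
- **Numbers.** Section 10.1 plans 50 patients, 25 per arm, with expected MRD-negative CR/CRi rates of 50% and 75%.

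**The concern.** Cutting a graded score into two groups treats all patients on the same side of the cut as alike. With 50 patients at most, that loss is a choice rather than a constraint, because the assay already delivers the finer measurement. Section 2.5.3 poses the question directly: whether PD-L1 on blasts correlates with response to the combination. The only test written specifically for that question is the dichotomised one.

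Two further gaps follow. With no stated cut-off, a threshold could be picked after outcomes are known. And one question has two planned analyses, the 2×2 test and the Part 1 regression, with no order between them, so the result to be reported as the PD-L1/response finding is not settled in advance.

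**Working it through.** **1. The plan's own figure.** The only power stated is for the primary endpoint: about 71% with 25 per arm, 50% against 75%, one-sided 0.1. Pooled z-test:

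Φ[(0.25·√25 − 1.2816·√(2·0.625·0.375)) / √(0.5·0.5 + 0.75·0.25)] = Φ[(1.25 − 0.877)/0.661] = Φ(0.563) = 0.713.

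It reproduces. No power or significance level is stated for the PD-L1 test.

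**2. Inputs.**
- From Section 10.1: n = 50, an upper bound on patients with an evaluable core; share of responders (0.50 + 0.75)/2 = 0.625. This uses the primary endpoint as a proxy, since 10.4.2.3 does not say which response it means.
- Assumed: standard normal score, logit of response linear in the score, two-sided 0.05, odds ratios of 1.5, 2 and 2.5 per SD.
- Share positive: 50% (median split), 32% and 15%. The last two are borrowed from the background on checkpoint expression in human AML samples, where PD-L1 up-regulation was 15% in CD34+ cells and, in PBMCs, up-regulation of PD-L1, PD-L2, PD-1 and CTLA4 "was observed in 32%, 12.9%, 39%, and 3% of AML samples, respectively". These are mRNA figures from a cited study, not immunofluorescence positivity. They serve only as a range.

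**3. Information kept by the cut.** Efficiency = φ(z_p)² / [p(1 − p)].

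| Positive | φ(z_p) | Efficiency | Information lost |
|---|---|---|---|
| 50% | 0.399 | 0.637 | 36% |
| 32% | 0.358 | 0.588 | 41% |
| 15% | 0.233 | 0.426 | 57% |

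If the uncut analysis had 80% power, the large-sample power after the cut is Φ[√efficiency·(1.960 + 0.842) − 1.960]. That is a loss of 19, 23 and 35 points respectively.

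**4. Simulated power at n = 50** (20,000 runs per setting; score test on the continuous marker against Pearson chi-square on the cut marker).

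| Odds ratio per SD | Continuous | Cut, 50% positive | Cut, 32% | Cut, 15% |
|---|---|---|---|---|
| 1.5 | 27% | 19% | 16% | 10% |
| 2 | 60% | 43% | 36% | 20% |
| 2.5 | 81% | 62% | 53% | 30% |

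Before rounding, the loss is about 7-17 points at 1.5 and 16-51 points at 2-2.5. With the effect reversed (odds ratios 0.5 and 0.4), the cut test also lost in every setting, by less at 15% positive: 60% against 34%, and 80% against 49%.

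**5. Step effect.** If the true relation is a jump exactly at the cut, with an odds ratio of 4 for positive against negative, the order reverses. The chi-square has 23% against 14% at 15% positive, and 51% against 32% at 32% positive.

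**6. Small cells.** The smallest expected count is 50·p·0.375, which is 9.4, 6.0 and 2.8 at 50%, 32% and 15% positive. Simulated null rejection stays near 5% (about 4.5-5% at 15% and 32% positive).

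**The case against.** The strongest reply is that the better analysis is already planned. Part 1 assigns logistic regression to baseline biomarkers and response, and lists PD-L1/PD-1 among the markers followed over time. Section 10.4.2.3 also plans mixed-effects modelling of PD-L1. This stands in part. A reader might infer that the plan commits to the weaker test, or that the loss touches all inference on PD-L1. The documents do not support that, because nothing ranks the chi-square above Part 1. But nothing ranks Part 1 first either, or says that it uses the continuous score.

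The other replies also have force:
- **Size.** The loss depends on a normal score, a near-linear effect, the effect size and the cut, none of which the documents give. With a threshold effect at the cut, the 2×2 test wins. So the information and power losses cannot be stated as fixed properties of the plan.
- **Importance.** A reader might take PD-L1 to be the leading candidate predictor. Section 2.5.3 says that no single biomarker predicts response, and calls tumour-infiltrating lymphocytes the most reliable.
- **Validity.** Sparse cells might suggest that the chi-square is invalid. Its simulated error rate is not inflated, and the smallest expected count falls below 5 mainly at 15% positive. This is a reason to prefer Fisher's exact test, which Parts 3 and 4 already allow for other comparisons, but a secondary one.
- **Data-driven cuts.** Section 10.6 withholds summary outcome data from the study team until the DSMB releases them. That limits the risk but does not remove it: the statistician is exempt, and the cut-off is still unstated.

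**Conclusion.** The concern holds in a limited form. The PD-L1-specific response test dichotomises a quantitatively imaged marker with no stated cut-off, and its order relative to the Part 1 regression is undefined. Under a roughly normal score and a roughly linear effect, the cut loses 36% of the information at a median split and 57% at 15% positive. With 50 patients, 62.5% responders and two-sided 0.05, this is about 7-17 points of power at an odds ratio of 1.5 per SD and 16-51 points at 2-2.5. The figures apply to the 2×2 test only, and a step effect at the cut would reverse them. The missing cut-off and the missing order of analyses are defects whichever model is true. The analysis is exploratory, carries no allocated alpha, and does not bear on the primary conclusion. The change is still worth making, because it alters a stated method at almost no cost.

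**What to change.** In Section 10.4.2.3:

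1. Name the Part 1 logistic regression of response on the continuous PD-L1 score (for example log-transformed) as the lead PD-L1/response analysis, reporting the odds ratio per SD with its confidence interval.
2. Keep the negative/positive table as secondary and descriptive. Define QIF, fix its cut-off before outcomes are seen, and use Fisher's exact test in place of the Pearson chi-square.

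Part 1 should state that PD-L1 enters on the continuous scale.

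The cost is a few sentences of wording. The imaging is already planned as quantitative, so no extra samples or patients are needed. The downside is some loss of power if the true effect is a pure threshold at the chosen cut; the retained table would still display such a pattern.

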10.4.2.4 Olink Assay

Inflammation is a key underlying factor for the pathophysiology of a wide range of diseases, including malignancies. The Olink inflammation biomarker panel provides a high-throughput, multiplex immunoassay enabling analysis of 92 inflammation-related protein biomarkers across 96 samples simultaneously. The objective is to investigate protein signatures associated with response and efficacy.

10.4.2.5 WES

The determination of the mutation load, a total number of nonsynonymous point mutations, by whole-exome sequencing (WES) was shown to be useful in predicting the treatment responses to cancer immunotherapy (Lyu, 2018). Tumor mutational burden (TMB), along with PD-L1

expression, is a useful biomarker for immune checkpoint blockade selection across certain cancer types and TMB determination correlated with WES (Chan, 2019). We will use massively parallel sequencing technology to sequence the genomic DNA of tumor cells (leukemic bone marrow) and normal cells (germline) obtained from patients with AML at baseline. Mutational load by WES will be correlated with clinic-pathological parameters such as response to treatment, survival and immune infiltrating profile, and T cell repertoire diversity and clonality.

10.4.2.6 RNA-seq

The MD Anderson CIMAC uses Agilent RNA isolation products for RNAseq. RNA will be prepared using suitable purification system depending on sample source (fresh or FFPE). RNA integrity of FFPE RNA will be assessed using either the Agilent 4200 TapeStation and High Sensitivity RNA ScreenTape or the Agilent 2100 Bioanalyzer and RNA 6000 Pico Chip. Either method will employ the region analysis method to determine the percentage of RNA in the sample that is >200 nt for each sample to be processed. It is necessary to have RNA molecules >200 nt for efficient library construction and this value for each sample will determine appropriate conditions at various steps in the workflow.

10.4.2.7 TCR-seq

One mechanism by which checkpoint inhibitors are thought to elicit their effects by broadening the TCR repertoire. We will perform high-throughput sequencing of the TCR Vb CDR3 regions on flow cytometrically sorted T-cell subsets to assess the effect of immunotherapy on the diversity of the T-cell repertoire and assess for correlation to clinical outcomes. TCR sequencing analysis may be performed using DNA from tumor tissues as well as PBMC. Briefly, 500 ng tumor DNA or 3-6 µg PBMC DNA will be subjected to high throughput TCR Vβ CDR3 sequencing on an Illumina HiSeq sequencer with at least 5-fold coverage by ImmunoSEQ™ sequencing (Adaptive Biotechnologies, Seattle, WA). TCR diversity and clonality (defined as $1 - (\text{entropy}) / \log_2(\#)$ of productive unique sequences, where the entropy term takes into account the varying clone frequency) will be calculated using a software by Adaptive Technologies. T-cell repertoire diversity and clonality will be correlated with clinic-pathological parameters such as response to treatment, survival, and immune infiltrating profile, as well as genomic profiles (total mutation burden, non-synonymous mutation burden, predicted neoantigen burden, clonal mutation burden and clonal predicted neoantigen burden). TCR profile generated from treatment-refractory tumors at the time of disease progression will be compared to data from pre-treatment tumor samples to explore the TCR repertoire evolution of these tumors under therapeutic pressure. The dynamic changes of TCR from PMBC, when longitudinal blood samples are available, will be correlated to response to immune checkpoint blockade or chemotherapy and survival.

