1.3 Exploratory Objectives

- 1.3.1 MRD assessment by duplex sequencing (DS) and comparing DS and multiparameter flow cytometry for MRD detection as an exploratory biomarker.
- 1.3.2 Assessment of immune-checkpoint expression and dynamic change of immune cell subsets in response to the combination of checkpoint-inhibition and backbone combination in AML.

- 1.3.3 High-throughput sequencing of the TCR Vb CDR3 regions on flow cytometrically sorted t-cell subsets to assess the effect of immunotherapy on the diversity of the t-cell repertoire and assess for correlation to clinical outcomes.
- 1.3.4 Investigation of protein signatures and RNA signatures associated with response and efficacy using O-link cytokine panel and RNA-seq, respectively
- 1.3.5 Determination of mutational load by whole exome sequencing to assess for correlation with clinical outcomes, immune infiltrating profile, and T cell repertoire diversity and clonality.
- 1.3.6 Correlate gut microbiome at baseline and changes in the microbiome with clinical response, both in standard chemotherapy and immunotherapy/chemotherapy therapy settings.
- 1.3.7 MRD assessment using duplex sequencing strategy for circulating cell-free tumor DNA and correlation with long-term outcomes.

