7	Whole Exome Sequencing	WES (tumor) CLIA: N	Exploratory Correlate with clinical response	DNA from Mononuclear cells from bone marrow aspirate	Baseline and at relapse	M	MDACC CIMAC [name] [name] [contact] [name] [contact] [name] [contact]
	Whole Exome Sequencing	WES (Germline) CLIA:N	Exploratory Correlate with clinical response	DNA from Skin punch biopsies for germline control	Baseline	M	MDACC CIMAC [name] [name] [contact] [name] [contact] [name] [contact]

NCI Protocol #: 10300

Version Date: April 10, 2025

8	RNA-Seq	RNA-Seq CLIA: N	Exploratory Correlate with clinical response	RNA from mononuclear cells from bone marrow aspirate in EDTA	Baseline and at relapse	M	MDACC CIMAC [name] [name] [contact] [name] [contact] [name] [contact]
---	---------	--------------------	--	---	-------------------------	---	---

Priority	Biomarker Name	Assay (CLIA: Y/N)	Use in the Trial and Purpose	Specimens Tested	Collection Time Points	Mandatory or Optional	Assay Laboratory and Lab PI
9	TCR-Seq	TCR-Seq CLIA: N	Exploratory Correlate with clinical response	DNA from mononuclear cells from bone marrow aspirate in EDTA	Baseline, end of consolidation, after 6 months of treatment, after 1 year of treatment, and at relapse	M/O (optional for the after 6 months of treatment and after 1 year of treatment time points)	Adaptive Biotechnologies working with MDACC CIMAC [name] [name] [contact] [name] [contact] [name] [contact]

Priority	Biomarker Name	Assay (CLIA: Y/N)	Use in the Trial and Purpose	Specimens Tested	Collection Time Points	Mandatory or Optional	Assay Laboratory and Lab PI
Blood-based Biomarkers							
1	MRD Status	Duplex Sequencing (DS) CLIA: N	Exploratory Exploratory Endpoint	Peripheral blood (EDTA)	Baseline Induction therapy phase: Days 14 and end of induction. Consolidation therapy phase: Post Cycle 1 and end of consolidation. Maintenance therapy phase: Every 3 months End of maintenance/observation phase for patients who do not progress.	M	To be shipped from [name]'s lab after completion of flow cytometry studies Molecular Oncology Laboratory at Fred Hutchinson Cancer Research Center [name] [contact]

Priority	Biomarker Name	Assay (CLIA: Y/N)	Use in the Trial and Purpose	Specimens Tested	Collection Time Points	Mandatory or Optional	Assay Laboratory and Lab PI
Blood-based Biomarkers							

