2	cfDNA	Duplex Sequencing (DS) CLIA: N	Exploratory Exploratory Endpoint	Peripheral blood (Streck)	Baseline Induction therapy phase: Days 14 and end of induction. Consolidation therapy phase: Post Cycle 1 and end of consolidation. Maintenance therapy phase: Every 3 months	M	To be shipped to [name] laboratory, Fred Hutchinson Cancer Research Center Molecular Oncology Laboratory at Fred Hutchinson Cancer Research Center [name] [contact]
3	Immune cell subset analysis	CytoF CLIA: N	Exploratory Correlate with clinical responses	PMBCs from blood collected in heparin	Baseline, end of consolidation, after 6 months of treatment, after 1 year of treatment, and at relapse	M	MDACC CIMAC [name] [name] [contact] [name] [contact] [name] [contact]
4	Olink	Olink CLIA: N	Exploratory Correlate with clinical responses	Plasma from blood collected in heparin (same collection as for immune cell subset analysis)	Baseline, end of consolidation, after 6 months of treatment, after 1 year of treatment, and at relapse	M	Mt. Sinai CIMAC [name] [contact]
5	TCR-seq	TCR-Seq CLIA: N	Exploratory Correlate with clinical responses	DNA from PBMCs from blood collected in EDTA or sodium heparin tubes	Baseline, end of consolidation, after 6 months of treatment, after 1 year of treatment, and at relapse	M	Adaptive Biotechnologies working with MDACC CIMAC [name] [name] [contact] [name] [contact] [name]

							[contact]
Stool based biomarkers							
1	Gut microbiome characterization	16sRNA V4 region sequencing of bacterial genomic DNA	
 • Exploratory Correlate with clinical response 	Stool (OMNIgene-GUT)	
 • Baseline • Post Cycle 1 Consolidation 	M	MDACC CIMAC [name]

* CyTOF, WES, RNAseq, TCR and Olink analyses will be performed using cells and plasma from a single BM aspirate.

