6.1.8 TCR-Seq

6.1.8.1 Specimen(s) Receipt and Processing at the EET Biobank

Upon receiving the bone marrow aspirate in EDTA tubes from the collection site, the EET Biobank will **pool all samples** from one timepoint together and prepare Plasma and mononuclear cells following CIMAC guidelines. Plasma aliquots will be stored in a -80°C freezer, and mononuclear cells will be stored in liquid nitrogen vapor phase.

Additionally, PBMCs from peripheral blood samples collected in EDTA or heparin tubes will also be used for this assay.

Nucleic acids will be co-extracted from bone marrow mononuclear cells and peripheral blood mononuclear cells. An aliquot of DNA will be used for each assay (i.e., for TCRseq in bone marrow aspirate and for TCRseq in peripheral blood).

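### TCR-seq is promised on flow-sorted T-cell subsets but specified on unsorted mononuclear-cell DNA measured by mass, so its diversity and clonality indices vary with T-cell content

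*Combined protocol and SAP*

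**What the plan says.** **Material promised.** Exploratory objective 1.3.3 specifies "High-throughput sequencing of the TCR Vb CDR3 regions on flow cytometrically sorted t-cell subsets". Sections 2.5.9 and 10.4.2.7 repeat this; the latter reads "We will perform high-throughput sequencing of the TCR Vb CDR3 regions on flow cytometrically sorted T-cell subsets". The stated purpose is to assess the effect of immunotherapy on repertoire diversity and its correlation with clinical outcomes.

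**Material specified.** The biomarker plan (5.8) lists the marrow specimen for TCR-seq as "DNA from mononuclear cells from bone marrow aspirate in EDTA" and the blood specimen as "DNA from PBMCs from blood collected in EDTA or sodium heparin tubes". Section 6.1.8.1 states "Nucleic acids will be co-extracted from bone marrow mononuclear cells and peripheral blood mononuclear cells", with an aliquot of the DNA going to each assay. Section 10.4.2.7 itself goes on to say "TCR sequencing analysis may be performed using DNA from tumor tissues as well as PBMC".

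**Input.** Section 10.4.2.7 sets input by mass: "500 ng tumor DNA or 3-6" micrograms of PBMC DNA.

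**Metric.** Clonality is one minus entropy divided by log2 of the number of unique productive sequences, calculated with vendor software. Diversity has no formula.

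**Use.** Diversity and clonality are to be correlated with response, survival and immune infiltration. Progression samples are to be compared with pre-treatment samples, and changes over time in blood related to response and survival. Part 1 of the exploratory analysis plan (under 10.4) adds mixed models with a Benjamini-Hochberg correction. No down-sampling, minimum template count or template covariate is given.

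**The concern.** There are two linked problems. First, the objective and the operating instructions describe different measurements. DNA extracted from all mononuclear cells cannot afterwards be separated into T-cell subsets, so the subset repertoires named in 1.3.3 do not follow from the procedure in 5.8 and 6.1.8.1.

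Second, in unsorted material a fixed mass of DNA is not a fixed number of T cells. Marrow composition differs between time points by design: entry requires at least 20% myeloid blasts in marrow and/or blood (3.1.1), and remission requires fewer than 5% marrow blasts (13.2.2). If the T-cell share moves as the blast share moves, the number of templates moves too, and with it every index that depends on sampling depth. A change in sample composition could then be reported as a change in the repertoire.

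**Working it through.** The plan gives no sample size, power or precision for TCR-seq, so there is no figure of its own to reproduce. The check asks whether the indices stay constant when the repertoire does.

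**1. Inputs.** From 10.4.2.7: 500 ng tumor DNA, 3-6 micrograms PBMC DNA, and the clonality formula. Assumed, because the documents do not give them: 6.6 pg DNA per cell, the T-cell fractions, Zipf clone-size distributions, and recovery of every T-cell template.

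**2. Templates sampled from marrow.** 500 ng / 6.6 pg = 500,000 / 6.6 = 75,758 cells. Templates = 75,758 × T-cell fraction:
- 5%: 3,788
- 20%: 15,152

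**3. Indices from one unchanged repertoire of 200,000 clones, 5% to 20% T cells.**

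| Zipf exponent | Richness | Ratio | Entropy (bits) | Clonality |
|---|---|---|---|---|
| 0.8 | 3,087 → 10,690 | 3.5 | 11.24 → 12.70 | 0.031 → 0.051 |
| 1.0 | 2,048 → 6,587 | 3.2 | 9.53 → 10.46 | 0.134 → 0.175 |

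At exponent 1.2 the richness ratio is 2.9. At exponent 1.0 with a wider contrast, 3% against 30%, richness goes from 1,318 to 9,151 and clonality from 0.120 to 0.188.

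**4. Why clonality is not protected by its denominator (exponent 1.0).** At 5%: 1 − 9.53 / log2(2,048) = 1 − 9.53 / 11.00 = 0.134. At 20%: 1 − 10.46 / log2(6,587) = 1 − 10.46 / 12.69, about 0.175. The denominator grew by 1.69 bits and entropy by 0.93, so the index rises. Richness and entropy suggest a broader repertoire while clonality suggests a less even one, and nothing in the repertoire has changed.

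**5. Sensitivity to repertoire shape (1,000,000 clones, 2% to 20% T cells).**
- Exponent 1.0: richness 1,013 to 7,672, clonality 0.089 to 0.152
- Exponent 0.8: richness 1,393 to 12,299, clonality 0.012 to 0.033
- Exponent 0.6: richness 1,504 to 14,474, clonality 0.0004 to 0.0033

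The direction is the same throughout. The clonality shift is very small for the flattest repertoire.

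**6. Blood.** The permitted input is a two-fold range. At an assumed 50% T cells, 3 micrograms gives 227,273 templates and 6 micrograms gives 454,545. For exponent 1.0 on 1,000,000 clones, richness is 72,321 against 123,088 and clonality 0.230 against 0.249.

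**7. Does down-sampling remove the drift?** With 200,000 clones, exponent 1.0 and 2,000 templates per sample, richness stays at 1,173-1,191 and clonality at 0.112-0.115 across T-cell fractions of 3% to 30%.

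**The case against.** A reader might go further and infer that responders will show an artefactual rise in diversity that is credited to pembrolizumab. The documents do not support that, for these reasons:

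- Clonality, the only index given a formula, rises along with richness, so the artefact does not point uniformly to broadening.
- Patients without CR/CRi after induction or after the first consolidation cycle leave the study (7.1.1, 7.1.2). Marrow TCR-seq is next taken at end of consolidation (5.8), so non-responders have no marrow change to compare. Section 10.4.2.7 ties the dynamic-change correlation with response to blood.
- The pre-treatment/progression comparison is not one of blast clearance, since disease is present at both times. It is exposed only where T-cell content differs.
- Blast clearance occurs in both randomized arms, and Part 3 of the exploratory plan compares trajectories between arms.

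These points stand, and they limit the concern.

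It would also be too strong to say that subset repertoires cannot be obtained. Mononuclear cells are stored frozen, and some text following 6.1.8.1 is not in the copy reviewed. What can be said is that no sorting step is described.

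Two mitigations are partial. CyTOF is run on the same aspirate at the same time points, so T-cell content is measured, but no adjustment is pre-specified. The vendor software may normalise for template number, but the documents do not say so. Finally, blast percentages do not determine T-cell fractions, so the size of the effect is assumed rather than derived.

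**Conclusion.** The point holds in a limited form. The documents contradict themselves on sorted versus unsorted material. For the unsorted DNA that the operating sections specify, richness, entropy and clonality depend on template number. Under the stated assumptions, 5% against 20% T cells raises richness about 2.9- to 3.5-fold; clonality rises from 0.134 to 0.175 at exponent 1.0 and from 0.031 to 0.051 at exponent 0.8. The direction was the same in every repertoire tried. The size rests on the assumed T-cell fractions, clone distributions, DNA per cell and full template recovery.

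The exposed analyses are within-patient changes over time, baseline correlations with outcome where T-cell content differs between patients, and the pre-treatment/progression comparison where it differs between samples. Same-time-point comparisons between randomized arms are biased only if T-cell content differs by arm. The endpoint is exploratory, and the primary analysis is unaffected.

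**What to change.** 1. **Reconcile the text.** Either delete the sorted-subset claim from 1.3.3, 2.5.9 and 10.4.2.7, or add the sorting step to 5.8 and 6.1.8. Both are valid repairs.
2. **If the DNA stays unsorted,** define richness, diversity and clonality in 10.4.2.7 as computed after down-sampling every sample to one common number of productive templates, with a stated minimum count below which a sample is not analysed.
3. **Add a sensitivity model** with template count or T-cell fraction as a covariate, and report it next to the main result.

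If the sorted claim is deleted, the cost is wording and one routine computing step, plus the loss of the samples with the fewest T cells; report how many are lost by arm and time point. Adding a sorting step would instead bring laboratory work.
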